### **5.3. Safety Population**

All participants receiving any study cigarettes will be included in the safety population. Participants who may have attended the screening and first baseline visit, and have been randomized, but did not actually receive any cigarettes will be excluded from the

safety population.

## 6. Trial Endpoints

### 6.1. Primary Endpoints

The Primary Aim of the extended exposure study is to compare the effects of cigarettes varying in nicotine yield on smoking rate. The primary endpoint is average CPD during Week 12. Additional measures addressing this aim are breath CO level, urinary cotinine concentration, nicotine dependence (Fagerström Test for Nicotine Dependence, Wisconsin Index of Smoking Dependence Motives) scores, nicotine withdrawal (Minnesota Nicotine Withdrawal Scale, Questionnaire of Smoking Urges), and the Cigarette Purchase Task (CPT).

- CPD will be collected by daily Interactive Voice Response (IVR) to assess cigarette use in the days since the last interview. This will yield a continuous record of cigarette use throughout the study. A weekly average will be obtained for analysis by averaging the daily CPD reports.
- Breath CO
  - Collected at baseline and weekly for the duration of the study
- Urinary cotinine concentration
  - Collected at the second baseline, Weeks 6 and 12
- Nicotine dependence and withdrawal
  - Collected at screening, the first baseline, every other week (even weeks for nicotine dependence, odd weeks for nicotine withdrawal) until study completion and the abstinence visit
- CPT
  - Collected at the second baseline and Weeks 2, 6, 12 and the abstinence visit for usual brand cigarette
  - Collected at Weeks 2, 6, and 12 and the abstinence visit for study cigarette
  - Breakpoint: the lowest price at which cigarette consumption is 0.
  - Elasticity of demand: the sensitivity of cigarette consumption to price increases.
  - Omax: the maximum daily expenditure for cigarettes.
  - Pmax: the price at which cigarette expenditure is maximized.
  - Intensity: cigarette consumption at the lowest price (\$0 cost).

### 6.2. Secondary Endpoints

- Measures of depression and anxiety
  - Collected at the second baseline and Weeks 1, 2, 3, 4, 5, 6, 7, 8, 9, 10, 11 and 12

- Beck Depression Inventory
  - Overall Anxiety Severity and Impairment Scale
- Adherence to assigned tobacco products
  - Collected through the daily IVR system
- Use of multiple nicotine products.
  - Collected through the daily IVR system
- Biomarkers of exposure to tobacco carcinogens
  - Collected at the second baseline and Weeks 6 and 12
- Study retention
- Quit attempts and spontaneous quitting
  - Assessed at weekly visits and at the 30-day post-intervention assessment

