In a randomized trial with smokers interested in quitting, participants were randomly assigned to one of three tobacco products with varying nicotine yield levels (0.3 mg cigarette, 0.05 mg cigarette, or 4 mg lozenge) (Hatsukami et al., 2010). They were instructed to use the assigned products for 6 weeks and to then make a quit attempt. After 6-weeks' use of the 0.05 mg nicotine yield cigarette, there was a 30% reduction in the number of cigarettes smoked per day, a 25% reduction in breath carbon monoxide (CO) levels, a 95% reduction in cotinine levels, and significant reductions in tobacco-specific carcinogens and other toxicants. These measures either did not change in the 0.3 mg condition or increased, likely due to compensatory smoking observed at that dose. Compensatory smoking was not observed among those abruptly switched to the VLNC (0.05 mg) cigarette. Importantly, smoking rates were still declining at the end of the study, suggesting the potential for more substantive reductions with longer exposure. In the proposed study on extended exposure (Study 2), we will lengthen the duration of the study period to 12 weeks to more fully characterize this time course. Whether these same patterns occur among disadvantaged women is a primary question that we are seeking to address in this proposal.

Effects of very low nicotine content (VLNC) cigarettes:

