At the end of the first baseline visit, participants will be trained to use the Interactive Voice Response (IVR) System, which will contact participants each day throughout the study and ask about their smoking behavior as well as withdrawal symptoms the week before and after randomization. We will also review the IVR adherence incentive program, which consists of \$1 per call plus a \$10 bonus for seven consecutive calls. Participants may be provided a study cell phone if they have unreliable telephone access, do not have enough monthly cell phone minutes or prefer not to use their own phone.

The IVR system is operated by TeleSage. To be enrolled in the IVR system, research staff will enter the participant's initials, telephone number, subject identifier, and visit dates into the IVR TCORS website. Identifying information (initials and telephone numbers) will not be extracted with the data by the bioinformatics group. Please refer to TeleSage's privacy statement and HIPAA compliance form for additional information.

Baseline 2 biological specimens:

- 1) Urine sample for smoking biomarker assessment:

Participants will be asked to provide a urine sample (first void of the day) at the second baseline session for biomarker assessment. Samples will be stored at temperatures no more than -80°C. The tobacco-specific carcinogen biomarkers are total NNAL and PAH. Total cotinine levels will also be assessed to measure daily nicotine exposure. Participants will be reminded with a phone call the day before the visit, those who forget will be asked to return to the lab with their first void

urine sample or staff can arrange to meet the participant off campus to pick up their urine sample.

Biomarker shipping and storage:

Biomarkers will be shipped quarterly to the University of Vermont Laboratory for Clinical Biochemistry Research ([name] Lab). The [name] Lab will serve as a central repository for all biomarker specimens and will be responsible for distributing specimens to the appropriate labs on a quarterly basis. Urine samples will be analyzed and stored at the University of Minnesota [name] Lab.

Study 2 Experimental Procedures

Experimental Period:

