5. PSS-4
6. PANAS
7. PUQE-24
8. COVID-19 Symptom Questionnaire
9. Respiratory Health Questionnaire (Study Weeks 2, 6, and 12 only)
10. Perceived Health Risks Questionnaire (Study Weeks 2, 6, and 12 only)
11. CPT – with reference to assigned cigarette (Study Weeks 2, 6, and 12 only)
12. Smoking Stages of Change Algorithm and Contemplation Ladder (Week 12 only)

In the event that the REDCap website is not functioning, the assessments will be administered aloud and participant answers will be recorded securely. The interviewer will enter the data into REDCap when it resumes functioning properly. A note indicating that REDCap was not functioning during the session should be recorded in the 'End of Visit Evaluation Form'.

Biological Samples to be collected (Study Weeks 6 and 12 only):

- 1) First void urine sample

Interactive Voice Response System:

Participants will continue to use the IVR system on a daily basis throughout the experimental period to record the number of study cigarettes smoked per day and use of non-study cigarettes, if applicable. During the first week after Baseline 2 (randomization), the IVR system will collect information about withdrawal symptoms.

Variable Incentive Program:

An incentive program has been developed with the goal of improving attendance at scheduled assessment sessions and encouraging honest self-reports regarding all nicotine/tobacco use.

Briefly, participants will receive a total of five tickets for each visit they attend after randomization. Participants will be instructed that these tickets correspond to attendance (three tickets) and honest reporting (two tickets). They will be further instructed that these tickets "could" be eligible for entry into a monthly drawing for prizes, but that only tickets that are "validated" will be eligible for prizes.

Since it is prohibitively expensive to test urine samples each week for each participant and because it is currently not feasible to detect with reasonable precision non-compliance based on biomarkers in the higher nicotine group, we plan to only validate the attendance tickets. Hence, each participant who attends their regularly scheduled weekly session will have a total of five validated tickets entered into the monthly drawing.

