To help protect the participant's privacy, [name], PhD, has received a Certificate of Confidentiality from the National Institutes of Health. With this certificate, the researchers cannot be forced to disclose information that may identify the participants, even by a court subpoena, in any federal, state, or local civil, criminal, administrative, legislative, or other proceedings. The researchers will use the Certificate to resist any demands for information that would identify the participants, except as explained below. The Certificate cannot be used to resist a demand for information from personnel of the United States Government that is used for auditing or evaluation of federally funded projects or for information that must be disclosed in order to meet the requirements of the Federal Food and Drug Administration (FDA).

The Certificate of Confidentiality does not prevent the participant or a member of their family from voluntarily releasing information about themselves and their involvement in the research. If an insurer, employer or other person obtains the participant's written consent to receive research information, then the researcher may not use the Certificate to withhold that information.

The Certificate of Confidentiality does not prevent the researchers from disclosing voluntarily, without consent, information that would identify the individual as a participant of the research project in instances such as evidence of child abuse or a participant's threatened violence to self or others.

Outcome Variables

Primary Endpoints for Study 1:

- 1) Nicotine withdrawal (i.e., MNWS)
- 2) Rank ordering of ability of each nicotine cigarette dose to substitute for usual brand dose cigarette

3) Establish cross-price elasticity for each nicotine dose

Primary Endpoints for Study 2:

- d. Number of cigarettes smoked per day: study cigarettes, combined study and non-study cigarettes
- e. Measure of exposure (i.e., urinary cotinine, expired breath CO, nicotine dependence)

Secondary Endpoints for Studies 1 and 2:

- 1) Measures of adherence: non-study cigarette use, drop-out rate
- 2) Measures of psychiatric symptoms: BDI, OASIS
- 3) Measures of discomfort/dysfunction: MNWS, QSU-brief
- 4) Measures of other health-related behaviors: weight (Study 1 only)
- 5) Measures of nicotine/tobacco dependence: FTND, WISDM-brief
- 6) Measures of tobacco exposure: CO, total nicotine equivalents, NNN, NNAL, minor alkaloids

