## **7.3. Primary Endpoint Analysis**

### **7.3.1. Primary Analysis**

The primary endpoint is CPD during Week 12, compared to the CPD at baseline. While the primary outcome is the mean total CPD, consisting of both study and non-study cigarettes, the analyses will be repeated examining only the CPD contributed by study cigarettes. CPD will be computed as the mean CPD calculated on a weekly basis. Data analysis will use repeated measures analysis of variance, with two conditions and two time points (baseline and Week 12). In addition, the analysis model will include a random effect for site, a random

participant effect and random error (within-subject error). Variance parameters will be estimated using restricted maximum likelihood method with the Satterthwaite approximation.

Because CPD will be measured weekly, additional analyses will be performed including data collected at all time points. The analysis will be conducted in a manner similar to that described above, with the exception that there will be 13 time points: baseline and Weeks 1 through 12. For these analyses, the variance-covariance structure will be specified as first-order autoregressive.

Additional outcomes include the CPT, breath CO level, urinary cotinine concentration, and nicotine dependence and withdrawal scores. These will be examined in a manner similar to that described above for CPD. Natural log transformations will be performed as needed so that ANOVA model assumptions of normality and equal variances hold. Geometric means in original units will be calculated as well. Note that not all outcomes are assessed at weekly in-person visits. The time points at which each outcome is assessed is described in Section 6.

Finally, several assessments will be made at baseline as well as at the abstinence visit, which occurs the day following the Week 12 assessment. At this visit, measures of craving and withdrawal will be completed. The analysis will be similar to that described above for the CPD comparing baseline CPD to that reported at the end of the trial. The analysis will deviate from that described only in the timing of the tasks, with the time points consisting of the baseline and the abstinence visits, rather than the baseline and Week 12 visits reported above.

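### Adherence, and the non-study cigarettes in the primary CPD total, rest on self-report; cotinine already assayed at Weeks 6 and 12 could check both in the VLNC arm

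*SAP*

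**What the plan says.** **Adherence.** SAP 6.2 lists "Adherence to assigned tobacco products" and gives the source of this endpoint as "Collected through the daily IVR system". The protocol's Outcome Variables list has "Measures of adherence: non-study cigarette use, drop-out rate". Neither names a biomarker. Adherence is Secondary Aim 1 in the protocol's Study 2 Statistical Methods. The per-protocol set in SAP 5.2 is defined by completing 12 weeks, not by adherence.

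**Primary outcome.** SAP 7.3.1 states that "the primary outcome is the mean total CPD, consisting of both study and non-study cigarettes". SAP 6.1 collects CPD by IVR; the protocol's Study 2 Statistical Methods allow IVR, timeline follow-back or both. All of these are self-report.

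**Cotinine.** Under Baseline 2 biological specimens, the protocol states: "Total cotinine levels will also be assessed to measure daily nicotine exposure". SAP 6.1 times urinary cotinine at the second baseline and Weeks 6 and 12. SAP 7.3.1 analyses it as a further outcome by condition. There is no cut-off, no adherence classification and no comparison with reported use.

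**Reasons given for not validating reports.** The Variable Incentive Program section says that weekly urine testing is too expensive and that "it is currently not feasible to detect with reasonable precision non-compliance based on biomarkers in the higher nicotine group". It later adds practical problems with shipping urine for prompt testing. Only attendance is validated.

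**The concern.** Women in Study 2 know whether they hold their own brand or a research cigarette. All participants are asked to refrain from non-study cigarettes and told that there is no penalty for using them (Study 2 Randomization). A VLNC woman who smokes her usual brand on the side and does not report it is counted as adherent, and her total CPD is too low. If this happens more under VLNC than under usual brand, the arm difference in the primary outcome moves in favour of VLNC and Secondary Aim 1 is overstated.

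The plan takes misreporting seriously elsewhere. It uses a bogus pipeline, asks staff to judge truthfulness about tobacco use at the end of screening and baseline visits, and stresses honest reporting at every visit. Yet the objective measure it already pays for is not set against the reports.

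**Working it through.** **1. Do the stated limits cover the planned samples?** The cost argument concerns weekly tests of every participant; the Week 6 and 12 samples are assayed for cotinine anyway. The precision argument is confined to the higher nicotine group. The shipping argument concerns prompt testing for prize draws, which an end-of-trial analysis does not need. None rules out using the existing results in the VLNC arm.

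**2. Does product accountability fill the gap?** The weekly inventory (Study 2 Baseline Procedures) and the Product Accountability Log count study packs. They bear on use of study cigarettes, but the SAP ties them to no endpoint, and they cannot show cigarettes obtained elsewhere.

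**3. How large is the cotinine signal from one hidden usual-brand cigarette a day?** Neither document gives a usual-brand yield (both tables say N/A), so three sets of assumptions are shown. Baseline is 12.1 CPD, from the sample size sections.

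(a) *Cotinine proportional to yield × CPD.* Usual brand is assumed at 0.8 mg, which the protocol gives only as an example of a normal-nicotine yield. VLNC is 0.03 mg, with 12.1 − 5 = 7.1 study CPD.
- Adherent: 7.1 × 0.03 / (12.1 × 0.8) = 0.213 / 9.68 = 2.2% of baseline.
- One hidden cigarette added: (0.213 + 0.8) / 9.68 = 10.5%.
- Ratio: about 4.8, or roughly 5-fold.

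(b) *Anchored on "a 95% reduction in cotinine levels"* in the earlier trial of a 0.05 mg cigarette. The total is held at 12.1 CPD and one cigarette is swapped.
- Adherent: 5%.
- One hidden cigarette: 0.05 × 11.1/12.1 + 1/12.1 = 4.6% + 8.3% = 12.9%.
- Ratio: about 2.6-fold.

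(c) *Anchored on the 70% fall* after the taper to 0.1 mg, under Extended-exposure studies.
- Adherent: 30%.
- One hidden cigarette: 0.30 × 11.1/12.1 + 1/12.1 = 27.5% + 8.3% = 35.8%.
- Ratio: about 1.2-fold.

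Proportionality fits one cited result and fails on another. For 0.05 mg with 30% fewer cigarettes it predicts 0.05 × 0.7 / 0.8 = 4.4% of baseline, against 5% reported. For 0.1 mg it predicts 0.1 / 0.8 = 12.5%, against 30% reported.

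**4. What could differential under-reporting do to the primary comparison?** No SD is stated, so the plan's 80% power cannot be reproduced, only solved backwards (two-sided 0.05 assumed): SD = 5 / [(1.960 + 0.842) × √(2/45)] = 8.47. The standard error of the difference is then 8.47 × √(2/45) = 1.79. Suppose there is no true difference and VLNC women omit on average b more cigarettes a day than usual-brand women. A simple two-sample z-test, standing in for the planned model, rejects with probability 1 − Φ(1.96 − b/SE) + Φ(−1.96 − b/SE).

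| b (CPD) | SD 6 | SD 8.47 | SD 10 |
|---|---|---|---|
| 1 | 12% | 8.7% | 8% |
| 2 | 35% | 20% | 16% |
| 3 | 66% | 39% | 30% |

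The documents give no value for b; the table shows sensitivity, not an estimate.

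**5. How should flagged women be handled?** Take an invented case in which half of VLNC women hide 3 CPD. Reported mean 7.1; true mean 7.1 + 0.5 × 3 = 8.6. Setting flagged women to baseline gives 0.5 × 7.1 + 0.5 × 12.1 = 9.6, so an error of 1.5 becomes 1.0 the other way. If they hide only one, the true mean is 7.6 and the imputed mean is still 9.6: an error of 0.5 becomes 2.0. Adding a range of cigarettes avoids this.

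**The case against.** The best defence is that the plan has safeguards and that cotinine is a rough tool. Pack returns, counselling, the bogus pipeline and the no-penalty message all discourage concealment. Cotinine and breath CO are compared by condition, so widespread usual-brand smoking would blunt the cotinine contrast. Cotinine reflects any nicotine source, does not count cigarettes and is measured after baseline only twice. Screening out other nicotine use relies on the same self-report that is in doubt. Under (c) above the signal is weak.

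Much of this stands. It is why the check should be a flag and a sensitivity analysis and should not replace the endpoint. It does not remove the gap: a group contrast cannot show whether women who report full adherence are in fact adherent, and the safeguards discourage concealment without measuring it. The 70% figure also comes from a 0.1 mg yield, more than three times the 0.03 mg used here.

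A reader might infer that the bias can arise in the VLNC arm only. The documents do not support that. The request to avoid non-study cigarettes applies to everyone, and usual-brand women receive a supply tied to their own smoking rate, so they too can smoke and omit extra cigarettes. A greater tendency under VLNC is plausible but not shown.

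**Conclusion.** The point holds as a low-cost improvement. Adherence and the non-study part of primary CPD rest on self-report, and a partial objective check already exists in the planned data for the arm where it is most informative. Under-reporting that is greater under VLNC would favour VLNC; its size is unknown. The one-cigarette signal ranges from about 1.2-fold to about 5-fold. The upper figure rests on an assumed 0.8 mg usual brand, strict proportionality and 7.1 study CPD, and should not be read as established. The documents give no within-woman variability of cotinine, so the error rates of any cut-off cannot be calculated from them.

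A reader might go further and conclude that the primary analysis is invalid or must be replaced. The documents do not support this: the comparison by assignment stands if reporting is equally good in both arms, and nothing in them shows that it is not.

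**What to change.** In SAP 6.2 and 7.4, add a biochemical adherence measure for the VLNC arm at Weeks 6 and 12:

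- Use each woman's ratio of cotinine to her Baseline 2 value. Fix one main cut-off before any data by condition are seen, and show results over a range of cut-offs. The one-cigarette values above (10.5% to 36% of baseline) are one possible range.
- Among VLNC women who self-report full adherence and no other nicotine use, report the share above the cut-off.
- Repeat the Week 12 total CPD analysis as a sensitivity analysis, adding a range of undisclosed cigarettes a day for flagged women, for example 1 to 3. State that this adjusts the VLNC arm only and can only reduce an apparent VLNC benefit. If baseline CPD is used for flagged women at all, label it as an extreme bound.
- Leave the primary analysis unchanged.

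The cost is SAP wording and a small analysis; no new visits, samples or assays are needed. The downside is an approximate cut-off on a marker that responds to any nicotine source, and the write-up should say so.

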### **6.3. Exploratory Endpoint**

- None at this point.

### **6.4. Safety Endpoints**

- Adverse events (AEs)
- Serious adverse events (SAEs)
- Birth outcomes
  - Live birth
  - Birth weight
  - Mother's gestational age at delivery
  - Type of nursery admission

## **7. Statistical Analysis**

### **7.1. General Approach**

To examine these Aims, repeated measures analysis of variance (ANOVA) will be used for outcomes that are measured on multiple occasions from baseline to the end of the intervention phase. Each repeated measures ANOVA model consists of five terms: cigarette condition, visit, interaction between cigarette condition and visit, a random effect for study site, a random participant effect (between-subject error), as well as random error (within-subject error). Variance parameters will be estimated using restricted maximum likelihood method with the Satterthwaite approximation. In the event of a statistically significant condition effect or a condition-by-visit interaction, post-hoc tests will be conducted in order to explore the nature of the significant findings.

### **7.2. Describing the Study Population(s)**

### **7.2.1. Baseline Characteristics:**

Baseline characteristics will be summarized by condition to identify any group imbalances post-randomization. This will include demographic characteristics (age, race/ethnicity), smoking characteristics (CPD, menthol status), and nicotine dependence, as well as the randomization scheme noted above. Continuous variables will be summarized by mean and standard deviation and compared by one-way analysis of variance, with variable transformations conducted as necessary to improve the normality of the distributions. Categorical variables will be summarized by frequencies and percentages and compared using the Chi-squared test.

